We applied this technology to melanoma patients on an immunotherapy trial and found that non-responders had more Granzyme B+ cells and molecules than responders. Notably, these cells did not secrete the delivery molecule perforin, demonstrating our ability to deeply characterize cells. Although our most developed data is in melanoma, these assays have been performed in lymphoma. In Hodgkins lymphoma (HL), our cytokine secretion analysis demonstrated that patients who fail therapy have higher levels of IL9 (p=0.0028) and IL22 (p=0.021) at diagnosis compared to those who respond to treatment. We have also identified a suite of cytokines that increase over the course of disease treatment (including IL4, IL5, IL10; p=0.001) only in patients who fail therapy (ASH abstract 128366).

1.53 Mantle cell lymphoma international prognostic index (IPI) prognostic score is a continuous variable derived from 4 factors including age, ECOG PS, LDH and WBC count, and classifies MCL patients into 3 risk groups (low-risk, intermediate-risk, and high-risk) with differential survival (33). Other markers at diagnosis that have been shown to be prognostic in MCL are Ki-67 proliferation index (34, 35) and complex cytogenetics (36). Complex karyotype is defined as 3 or more detectable chromosomal abnormalities. Ki-67 staining performed on the tissue biopsy at diagnosis will be used to calculate the proliferation index, defined as the percentage of Ki-67 positive lymphoma cells, and to categorize patients into < 10%, 10-30% and > 30% subgroups. The MIPI score, proliferation index and complex cytogenetics status at MCL diagnosis will be correlated with the MRD rate prior to the 4th cycle of the proposed regimen. The interim MRD positivity alone and also in combination with the at-diagnosis prognostic factors will be tested for association with the treatment response at EOI according to the Lugano 2014 response criteria based on PET-CT scans.

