2.3 Correlative Research

- 2.31 To evaluate changes in minimal residual disease (MRD) status in both responding and non-responding patients at EOI and end of maintenance and compared to baseline as well as correlate MRD status with PFS and OS.
- 2.32 To evaluate changes in systemic immune profiles and T cell activation induced by treatment with RSc+Pola+Ven.
- 2.33 To evaluate the prognostic importance of high-risk cytogenetic alterations, and other risk stratification scores in patients with relapsed/refractory MCL receiving RSc+Pola+Ven.
- 2.34 To evaluate features of the tumor microenvironment in patients with relapsed/refractory MCL receiving RSc+Pola+Ven.
- 2.35 To evaluate molecular features associated with response in PDX models from patients with relapsed/refractory MCL receiving RSc+Pola+Ven.

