12.0 Descriptive Factors

12.1 International Prognostic Index (IPI) [Shipp et al, 1993]: low risk (0 or 1 risk factors) vs. low intermediate (2 risk factors) vs. high intermediate (3 risk factors) vs. high (4 or 5 risk factors)

Risk Factors	0 points	1 point
Age	≤ 60 yrs.	> 60 yrs.
Serum LDH	≤ 1 x normal	> 1 x normal
ECOG PS	0 or 1	≥2
Stage	I or II	III or IV
Extranodal involvement	≤1 site	>1 site

Total number of risk factors = sum of the number of points for each prognostic factor.

Mantle Cell Lymphoma International Prognostic Index (Formula-based MIPI): Scores determine risk group: Low risk (<5.7) vs. Intermediate risk (≥5.7-<6.2) vs. High risk (≥6.2).

The MIPI score is calculated by this formula: $[0.03535 \times \text{age (years)}] + 0.6978$ (if ECOG > 1)+ $[1.367 \times \log_{10}(\text{LDH/ULN})]$ + $[0.9393 \times \log_{10}(\text{WBC count per }\mu\text{L})]$.

Note: The MIPI score will be calculated in Rave once the components are entered.

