- 16.327 MRD Analysis: MRD will be assessed on whole blood using the Roche panel at pre-treatment, end of induction, and end of maintenance.

 MRD status for both responders and non-responders at each time point will be reported descriptively and explored for correlation with clinical factors and patient outcomes such as PFS and OS. Changes in MRD status from baseline to end of induction and end of maintenance will also be summarized.
- 16.328 T cell and cytokine subsets: Systemic immune profiles and T cell activation will be investigated using multi-parameter flow cytometry, and cytokine analysis in the peripheral blood of patients at the following timepoints: a) pre-treatment, b) early in treatment (cycle 3), c) end of induction (cycle 7), d) end of maintenance year 1 (cycle 18), f) end of maintenance year 2. The results from T cell and Cytokine subsets analysis will be reported descriptively by median, min, max, and interquartile range.
- 16.329 High risk cytogenetic alterations and other risk stratification scores will be summarized using frequency and percentages.

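### Objective 2.33 asks whether cytogenetics and risk scores are prognostic, but Section 16.329 only counts them, and the one association described in Section 1.53 depends on an MRD sample that is not scheduled

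*Combined protocol and SAP*

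**What the plan says.** Section 2.3 lists among the correlative goals: "To evaluate the prognostic importance of high-risk cytogenetic alterations, and other risk stratification scores in patients with relapsed/refractory MCL receiving RSc+Pola+Ven". Section 16.329 answers it with: "High risk cytogenetic alterations and other risk stratification scores will be summarized using frequency and percentages". Section 16.326 labels the correlative analyses exploratory because the sample is small.

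The background goes further. In Section 1.53 the MIPI score, the Ki-67 proliferation index and complex cytogenetics at MCL diagnosis "will be correlated with the MRD rate prior to the 4th cycle of the proposed regimen". Interim MRD positivity, alone and "in combination with the at-diagnosis prognostic factors will be tested for association with the treatment response at EOI", is the second analysis described there. No method is named for either.

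On MRD timing, Section 16.327 says: "MRD will be assessed on whole blood using the Roche panel at pre-treatment, end of induction, and end of maintenance". Section 12.0 defines IPI and MIPI as descriptive factors and notes: "The MIPI score will be calculated in Rave once the components are entered". It does not say which visit supplies the components.

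**The concern.** Prognostic importance is a relation between a baseline factor and a later outcome. Counting patients in each risk category describes the case mix; it gives no risk difference, odds ratio or hazard ratio. A team that follows Section 16 exactly would finish the trial with a table of risk groups and no statement on whether they predict response or survival on this regimen. Any prognostic result reported later would rest on factors, cut-points and outcomes chosen after the data were seen. The exploratory label in Section 16.326 governs how results are read, but it does not supply an analysis.

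**Working it through.** The plan gives no figure for this point, so the check is a comparison of texts, followed by arithmetic on what an added analysis could deliver.

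**1. Does any other item in Section 16 link these factors to outcome?**

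- 16.321, 16.323 and 16.324: the Fisher and log-rank comparisons of ORR, PFS and OS are by ibrutinib exposure only.
- 16.327: MRD status is explored against clinical factors and against PFS and OS. If clinical factors include risk scores, the link is from score to MRD, not from score to outcome.
- 16.72: subset looks are by race and gender.

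None relates cytogenetics, MIPI or IPI to CR, PFS or OS.

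**2. Does Section 1.53 fill the gap?** It needs MRD before cycle 4. The test schedule (Section 4.0) puts the optional MRD blood at day 1 of cycle 1, EOI and end of maintenance. Section 14.1 and Section 16.327 give the same three time points. The analysis also never takes the factors on their own against response, does not mention PFS or OS, and is not carried into Section 16.

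**3. Which inputs are available?**

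- MIPI: age, ECOG PS, LDH and WBC. ECOG PS is assessed within 30 days, and blood counts and chemistry (including LDH) within 14 days, before registration.
- IPI: age, LDH and ECOG PS, plus stage and extranodal sites. A PET-CT is done within 30 days before registration.
- Ki-67 and karyotype: neither is in the test schedule or Section 12.0. Eligibility criterion 3.12 needs cyclin D1 by IHC or t(11;14), not Ki-67 or a full karyotype. Section 17.41 stores tissue for future analysis, and Section 17.46 says no genetic specimens are collected from tissue. Pathology reports uploaded under Section 18.5 may contain these results, but no planned capture is shown.

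**4. Precision for a CR difference.** Assumptions: 46 evaluable MCL patients (the maximum in Section 16.22) and CR of 35% in both groups. The documents give no risk-group prevalence, so several splits are shown. Half-width = 1.96 × √[0.35 × 0.65 × (1/n₁ + 1/n₂)].

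- 23 vs 23: 1.96 × √(0.2275 × 2/23) = 0.276, about 28 points.
- Three equal groups (MIPI, Ki-67), about 15 each: 1.96 × √(0.2275 × 2/15) = 0.341, about 34 points.
- 9 vs 37: 1.96 × √(0.2275 × (1/9 + 1/37)) = 0.347, about 35 points.
- Four equal groups (IPI), 11.5 each: 1.96 × √(0.2275 × 2/11.5) = 0.390, about 39 points.
- 8 vs 8, if only 16 patients are evaluable, at the same rate: 1.96 × √(0.2275 × 2/8) = 0.467, about 47 points. A stop under Section 16.211 requires 3 or fewer CRs in 16, so little could then be said about CR by risk group.

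**5. Power of formal tests (two-sided 0.05, N = 46, assumed rates).** For CR of 15% vs 45% by a binary factor, Fisher power is 0.28, 0.45 and 0.51 at splits of 9/37, 14/32 and 23/23. For 25% vs 40% it is 0.07 to 0.12. For PFS or OS, SE(log HR) = 1/√[D·p(1−p)]. With D from 20 to 40 events and prevalence p from 20% to 50%, power for HR 2 runs from 0.24 to 0.59, and the HR detectable with 80% power runs from 4.8 down to 2.4.

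**6. Effect on the primary design.** None. The rule (stop at 3 or fewer of 16; promising at 11 or more of 46) gives exact type I error 0.0486 and power 0.8506 at 35%, against the stated 0.049 and 0.851.

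**The case against.** The strongest reply is that this is one correlative goal among several, declared exploratory, with no bearing on a primary or secondary endpoint, a decision rule or a safety rule. That stands, and it sets the severity.

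A second reply is that Section 1.53 already plans an association with EOI response. It does, so a reader who infers that the protocol nowhere connects these markers to outcome goes too far. A joint analysis with MRD could yield marker-response estimates. What defeats it is the missing MRD time point. Optional immunology research blood is drawn on day 1 of cycle 3 (Section 4.0, note 12), which falls before cycle 4. However, Section 14.41 stores research blood for future work, and no MRD test is assigned to that draw.

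A reader might also infer that all the data are in hand and only the analysis text is at fault. The documents support that for MIPI, IPI and the outcomes, but not for Ki-67 or karyotype.

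Finally, nothing in the documents shows that values at diagnosis are invalid as prognostic factors. Registration values are proposed for MIPI and IPI because PFS and OS are counted from registration and the components are measured then.

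**Conclusion.** The mismatch holds. Section 16.329 cannot answer objective 2.33, no other item in Section 16 does, and the association in Section 1.53 cannot be run as written. Severity is minor. The achievable gain is descriptive: estimates with wide intervals, roughly 28 to 39 points either side for a CR difference with 46 patients, depending on the split. These widths rest on an assumed CR near 35%, equal rates across groups and assumed splits. At that size, hypothesis tests would mostly be uninformative, so estimation labelled exploratory is the right form. The documents do not support a stronger conclusion that the trial's efficacy result is compromised.

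**What to change.** Keep the frequency summary in Section 16.329 and add:

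> In MCL patients treated at the final dose level, EOI CR will be reported with exact 95% CIs by MIPI and IPI risk group calculated from registration values. PFS and OS will be estimated by Kaplan-Meier for the same groups, with a univariable Cox hazard ratio and 95% CI for MIPI as a continuous score. The same summaries will be given for Ki-67 group and complex karyotype in patients with an available result, stating the number available and the time point of the sample. All results are exploratory.

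Then reconcile Section 1.53 with the MRD schedule: either remove the pre-cycle-4 MRD analysis or use the EOI MRD that is collected. In the second case, EOI MRD and EOI response are measured at the same time, so their association is concordance rather than early prediction, and only patients who consented to the optional sample contribute.

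Rewording objective 2.33 as descriptive would also remove the contradiction, but it gives up an answer that the MIPI, IPI and outcome data can provide.

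The cost is a few sentences and a small analysis, with no new visit or sample for MIPI and IPI. The downside is several more imprecise exploratory estimates, and Ki-67 and karyotype results that may be incomplete because no capture is planned.

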16.4 Early Safety Analysis

The first cohort of three patients will be treated at the starting dose level of Venetoclax (400 mg days 1-21) and observed for at least 63 days (3 cycles) from the start of treatment to assess toxicity. If significant toxicity as defined in section 7.7 is observed in 0 or 1 of these 3 patients, 3 new patients will be accrued and treated at same dose level of Venetoclax (400 mg days 1-21) and observed for 3 cycles. After enrolling 6 patients on Venetoclax dose level of 400 mg days 1-21, if \leq 1 patient experience significant toxicity, then this dose will be considered safe and rest of the patients in expansion cohort will be treated at this dose level of Venetoclax.

However, if 2 or more out of the first 3 or 6 patients experience significant toxicity, then the dose of venetoclax may be de-escalated to 300 mg days 1-21 (Dose Level -1, Table 8.21). In this case, another safety analysis using similar 3+3 design approach will be conducted at the reduced dose level of venetoclax.

Safety will be assessed through summaries of adverse events and changes from baseline laboratory results. All adverse events occurring on or after first study treatment will be summarized by NCI CTCAE v5.0 grade. Deaths reported during the treatment period and during post-treatment follow-up will be listed and summarized.

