10.52 Baseline and Adverse Events Evaluations

The following pre-treatment symptoms/conditions are to be graded at baseline and at each evaluation using CTCAE v5.0 grading.

System Organ Class (SOC)	Adverse Event/Symptoms	Baseline	Each evaluation
Nervous system disorders	Peripheral Sensory Neuropathy	X	X
Blood and lymphatic system disorders	Anemia	X	X
Investigations	Neutrophil count decreased	X	X

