10.53 Case Report Forms - Academic and Community Cancer Research United (ACCRU)

Submit the following AEs not specified in Section 10.5. Submit via appropriate Academic and Community Cancer Research United (ACCRU) Case Report Forms (i.e., paper or electronic, as applicable) the following AEs experienced by a patient and not specified in Section 10.5:

- 10.531 Grade 2 AEs deemed *possibly, probably, or definitely* related to the study treatment or procedure.
- 10.532 Grade 3 and 4 AEs regardless of attribution to the study treatment or procedure

10.533 Grade 5 AEs (Deaths)

- -Any death $\underline{\text{within 30 days}}$ of the patient's last study treatment or procedure regardless of attribution to the study treatment or procedure requires expedited reporting within 24-hours .
- -Any death more than 30 days after the patient's last study treatment or procedure that is felt to be at least possibly treatment related must also be submitted as a Grade 5 AE, with a CTCAE type and attribution assigned.
- 10.54 Late occurring adverse events are any adverse events that occur during Clinical

- Follow-Up and Survival Follow-Up reporting periods. These are reported in compliance with Section 4.0 and Section 18.0.
- 10.55 Reconciliation: ACCRU agrees to conduct reconciliation for the product. Genentech and ACCRU will agree to the reconciliation periodicity and format but agree at maximum to exchange quarterly line listings of cases received by the other party. If discrepancies are identified, the Sponsor and Genentech will cooperate in resolving the discrepancies. The responsible individuals for each party shall handle the matter on a case-by-case basis until satisfactory resolution.
- 10.56 Quarterly Report: ACCRU will provide Genentech with accrual and a toxicity report on a quarterly basis.
- 10.57 IND Annual Reports: All IND annual reports submitted to the FDA by the Sponsor-Investigator should be copied to Genentech.

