16.32 Secondary Outcome Analysis

- 16.321 The overall response rate (ORR) at the end of induction will be estimated by the total number of patients who achieve a CR or PR by PET-CT scans according to Lugano 2014 divided by the total number of evaluable patients. All evaluable patients will be used for this analysis. Exact binomial 95% confidence intervals for the true overall response rate will be calculated. The ORR between ibrutinib-naive and ibrutinib-pretreated patients will be compared using Fisher's exact test.
- 16.322 The Best Response Rate to maintenance therapy will be evaluated. CR, PR and SD rates for patients who continue to maintenance will be estimated by number of patients who continue on maintenance therapy and achieve CR, PR or SD, respectively, at the end of maintenance divided by the total number of evaluable patients who continue to maintenance. Conversion rate from PR to CR will be evaluated by the number of patients achieving CR at EOM divided by the total number of patients who continue to maintenance in PR. Conversion rate from SD to PR or SD to CR will be evaluated by the number of patients achieving PR or CR, respectively at EOM divided by the total number of patients who continue to maintenance in SD.
- 16.323 Progression free survival (PFS) is defined as the time from registration to the earliest date of documentation of disease progression by CT or

- PET/CT or death due to any cause. The distribution of progression-free survival will be estimated using the method of Kaplan-Meier⁴. The PFS between ibrutinib-naive and ibrutinib-pretreated patients will be compared using log-rank test.
- 16.324 Overall survival (OS) is defined as the time from registration to death due to any cause. The distribution of OS will be estimated using method of Kaplan-Meier. The OS between ibrutinib-naive and ibrutinib-pretreated patients will be compared using log-rank test.
- 16.325 AEs: All eligible patients that have initiated treatment will be considered evaluable for assessing AE rate(s). The maximum grade for each type of AE from each patient will be used for analysis, and frequency tables will be reviewed to determine patterns. Additionally, the relationship of the AE(s) to the study treatment will be taken into consideration.
- 16.326 Correlative Analysis: Due to the small overall sample size, the results of these analyses will be considered exploratory and hypothesis- generating in nature.

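### The by-grade summary of all adverse events in Section 16.4 cannot be built from what Section 10.53 collects: low-grade events are under-counted for most terms, and baseline neuropathy may be counted as toxicity

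*Combined protocol and SAP*

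**What the plan says.** On analysis, Section 16.4 states: "All adverse events occurring on or after first study treatment will be summarized by NCI CTCAE v5.0 grade". It sets no limit by grade or attribution. Section 16.325 fixes the unit of analysis: "The maximum grade for each type of AE from each patient will be used for analysis". It adds that "the relationship of the AE(s) to the study treatment will be taken into consideration", without saying how.

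On collection, Section 10.53 opens with "Submit the following AEs not specified in Section 10.5" and lists three classes:

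- For Grade 2, item 10.531 sets a limit by attribution: "Grade 2 AEs deemed *possibly, probably, or definitely* related to the study treatment or procedure".
- For the next two grades, item 10.532 sets no such limit: "Grade 3 and 4 AEs regardless of attribution to the study treatment or procedure".
- For Grade 5, item 10.533 covers deaths within 30 days of the last treatment or procedure whatever the attribution, and a later death only if it is one "that is felt to be at least possibly treatment related must also be submitted as a Grade 5 AE".

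Section 10.52 is separate. For peripheral sensory neuropathy, anemia and decreased neutrophil count, it says: "The following pre-treatment symptoms/conditions are to be graded at baseline and at each evaluation using CTCAE v5.0 grading". It sets no threshold of grade or attribution.

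Section 10.41 adds events of special interest at any grade (transaminase increases listed under potential drug-induced liver injury, tumor lysis syndrome, treatment-related secondary malignancy). It also adds Grade 1-2 serious events that lead to hospitalization of 24 hours or more. Section 10.1(g) says expedited events must go through routine reporting as well.

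**The concern.** The analysis text and the collection text describe different sets of events. A table built as Section 16.4 describes would be headed as covering everything, yet most of its Grade 1 cells would be empty because nobody was asked for those events. Its Grade 2 column would mean related events, and its Grade 3-4 column would mean events from any cause.

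The solicited terms have a different problem. They are graded at every evaluation, and Section 16.325 takes the maximum without mentioning the baseline grade. Exclusion 3.29d bars neuropathy only above Grade 1, so a patient may enter with Grade 1.

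At stake are the toxicity rates reported for secondary objective 2.25, which Section 16.6 says will be posted publicly with the other secondary endpoints. Section 1.4 rests part of the case for the regimen on tolerability. Neuropathy matters in particular, because Section 1.231 names forms of it as the most frequent events leading to discontinuation of polatuzumab vedotin.

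**Working it through.** The plan gives no figure to reproduce. The check sets the collection rules side by side, by grade, attribution and route.

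| Grade | Most terms, at least possibly related | Most terms, unlikely or unrelated | Three 10.52 terms | Special-interest events; serious events with hospitalization of 24 hours or more, within 30 days of last dose |
|---|---|---|---|---|
| 1 | not required | not required | graded at baseline and each evaluation | required |
| 2 | required (10.531) | not required | graded at baseline and each evaluation | required |
| 3-4 | required (10.532) | required (10.532) | required | required |
| 5 | required (10.533) | only if within 30 days of last treatment | as for other terms | as for other terms |

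The Grade 3-4 row is complete. The Grade 1 and Grade 2 rows are not, except in the last two columns.

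Now apply the maximum-grade rule of Section 16.325 to four patients:

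1. Worst nausea is Grade 1, related, not serious. Nothing is submitted, so the patient appears to have had no nausea.
2. Worst nausea is Grade 2, judged unlikely related, not serious. Nothing is submitted, and the patient again appears event-free.
3. Worst nausea is Grade 3, judged unlikely related. It is submitted and counted at Grade 3.
4. Neuropathy is Grade 1 at entry and stays Grade 1. It is graded at each evaluation, so its on-study maximum is Grade 1. Section 16.325 does not say whether it counts.

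Patients 2 and 3 have the same attribution, but only one is counted. That is the mixture of definitions. Considering relationship at analysis cannot restore patients 1 and 2, because their events were never requested.

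The direction of each bias follows, but not its size:

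- For an unsolicited term with true any-grade rate r, let g be the share of affected patients whose worst event is a non-serious Grade 1 or an unrelated, non-serious Grade 2. The table then shows r x (1 - g), which is below r whenever g is above 0. The documents give no g.
- For neuropathy, let b be the fraction entering at Grade 1 and w the share of them who worsen. If baseline is ignored, the over-count is at most b x (1 - w), since worsening is a genuine on-treatment event. The documents give neither b nor w.

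Two further details affect the correction. For special-interest events, the reporting table in Section 10.41 asks for the adverse event form only if the Section 10.5 criteria are met, which does not fit Section 10.1(g). These events may therefore be missing from the routine dataset even though they are reported. Also, the Grade 5 row is not fully all-cause, although Section 16.4 separately lists deaths during follow-up.

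Finally, the decision rules. Section 16.522 uses related Grade 4 non-hematologic events, discontinuations for Grade 3-4 hematologic events, and related Grade 5 events. Section 7.7 is built mainly on Grade 3-4 events. All of these are collected, as is a related Grade 2 event that delays cycle 2.

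**The case against.** Several counter-arguments have force.

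- **Grade 1 is not wholly absent.** A reader of Section 10.53 alone might infer that the tables hold no Grade 1 events. The documents do not support that, because Sections 10.52 and 10.41 bring some in. This stands, and the point is limited to most terms.
- **Routine reporting of listed expected events.** Section 10.31 says events such as fatigue up to Grade 3 must still be reported routinely. But its heading concerns serious events exempt from expedited reporting, and it points back to Section 10.53. It does not clearly widen collection.
- **The objective is regimen-related toxicity.** Leaving out unrelated Grade 2 events fits objective 2.25. This stands for the objective, but not for Section 16.4, which promises everything. Related Grade 1 events are missing too.
- **Baseline is partly covered.** Section 16.4 also plans laboratory changes from baseline, which helps for anemia and neutrophils but not for neuropathy. Nor does the plan say that unchanged pre-existing grades will be counted. The fault is an unstated rule, not a stated wrong one.
- **A numerical bias is tempting.** Section 1.231 gives 30-43% for fatigue, diarrhea and nausea in two polatuzumab combination studies. If 50-70% of such events were Grade 1, the table would show between 30% x 0.3 = 9% and 43% x 0.5 = 21.5%. The documents give no such share, do not label those rates as any-grade, and plan no comparison with them. Similarly, if 20-30% of patients entered with Grade 1 neuropathy, 20-30 points would be only the upper bound on the over-count, and that entry share is also unsourced.
- **The forms are not in the documents.** The case report form packet and Data Submission Schedule may ask for more than Section 10.53.

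**Conclusion.** The mismatch is real and can be read directly from the text. Followed as written, the plan under-counts low-grade toxicity for most terms, mixes related-only Grade 2 with all-cause Grade 3-4, and leaves open whether pre-existing Grade 1 neuropathy counts as toxicity. The direction is clear; the size cannot be given.

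The effect stops at the descriptive safety tables. A reader might infer that the 3+3 decision or the stopping rules are weakened, but the events they mainly rest on are captured. The severity is minor.

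The conclusion assumes that the case report form packet and Data Submission Schedule ask for no more than Section 10.53. If they ask for more, Section 10.53 is the text to correct, and an edit is still needed.

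**What to change.** In Sections 16.4 and 16.325, define the summarized events as adverse events submitted under Sections 10.4 and 10.5, in place of the reference to all events. Then tabulate:

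- (a) Grade 2 or higher, at least possibly related;
- (b) Grade 3 or higher regardless of attribution, with a footnote that deaths more than 30 days after last treatment enter as Grade 5 events only if at least possibly related;
- (c) the three Section 10.52 terms at all grades, counting only worsening over the baseline grade;
- (d) special-interest and serious events at any grade, listed separately.

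Footnote the collection thresholds under each table and report no any-grade rates for other terms. The cost is a few more tables and some wording. The data needed are already requested, including the baseline grades.
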